#### 10.4 Reporting of SAEs

In the case of a Serious Adverse Event, an SAE Form must be completed as soon as possible and faxed to [name]. This should be done within 24 hours of becoming aware of the event. If the SAE has not been reported within the specified timeframe, a reason for lateness must be provided when sending the SAE Form.

Each separate SAE episode must be recorded. For example, if an SAE resolves completely or resolves to baseline and then recurs or worsens again, this must be recorded as a separate SAE. For SAEs to be considered intermittent, the events must be of similar nature and severity.

SAEs for which there is no reasonable possibility of being drug related to one or both of the IMPs should be reported by completing sections 1-5 and the Reporting Information in section 10 of the SAE Form. Sites must provide data that is minimal for the assessment of the SAE, including: reason for seriousness, causality, event term and a narrative of the event.

All other SAEs (where there is at least reasonable possibility of it being related to trial medication) i.e. SARs - should be reported by completing all sections of the SAE Form.

On receipt of the SAE Form, the Trial Office staff will check the SAE Form for minimal criteria, then log the SAE and allocate it an identifying number. The Trial Office will confirm receipt of the SAE by sending a copy of the SAE log to the site within 24 hours of receipt. If the site have not received notification of receipt within 24 hours, it is the responsibility of site staff to confirm that the Trial Office have received the SAE form. For SARs the Trial Office will send the SAE Form to a clinical review panel who will give their opinion on the Site Investigator's classification of the SAR with respect to seriousness, causality and expectedness.

#### 10.5 Suspected Unexpected Serious Adverse Drug Reactions (SUSARs)

A Suspected Unexpected Serious Adverse Drug Reaction (SUSAR) is a serious adverse reaction, the nature or severity of which is not consistent with the applicable product information (e.g. Investigator's Brochure for an unapproved investigational product or SmPC for an approved product). SUSARs therefore are suspected to be at least possibly related to the study agent, fulfil the definition of a SAE, but the nature and severity of which are not consistent with the applicable product information.

All SUSARs must be reported to the responsible Authority and main REC by the Trial Office within the required timelines:

- Fatal or life threatening SUSARs will be reported within 7 days of the Trial Office receiving the initial report. Any additional information will be reported within eight days of sending the first report.
- All other SUSARs will be reported within 15 days of the Trial Office receiving the initial report.

The Trial Office will report SUSARs according to their SOPs. In addition, other safety issues may qualify for expedited reporting where they might materially alter the current risk assessment of an IMP or be sufficient to change IMP administration or the overall conduct of the trial.

#### 10.6 Follow-up of Serious Adverse Events

If new or amended information on a reported SAE becomes available, the Investigator should update the existing form, without obscuring any initial information. All new data must be initialled and dated so that all changes are clearly identified.

Follow-up will continue until all the necessary safety data for the event has been gathered. Any SAE that is ongoing when a subject completes his/her participation in the trial must be followed until any of the following occurs:

- The event resolves or stabilizes;
- The event returns to baseline condition or value (if a baseline value is available);
- The event is attributed to other agent(s) or to factors unrelated to study conduct.

## 10.7 Reporting Adverse Events on the CRF

Adverse events (non-serious) need only be recorded if the event leads to the patient withdrawing from study medication. Details must be recorded on the End of Treatment Form.

### **Terms and Grading of Events**

The NCI CTCAE Version 4.0 (currently up to Version 4.03) must be used to report AEs and where possible use the Lowest Level Terms provided. Where indicated on the form, provide the severity grade for each AE/SAE.

## 10.8 Events exempt from being reported as AE/ SAEs

### **Progression of underlying disease**

Trial endpoints will be reported on Follow-Up CRFs and are not be required to be reported as an SAE.

### **Death on study**

Provided it is not as a result of an SAE, then a death during the course of the study should be recorded on the Death CRF. Deaths arising from SAEs should be reported using the SAE Form.

## 10.9 Informing Investigators of new safety information

The Trial Office or the Chief Investigator will ensure that all investigators are kept informed in a timely manner as new safety profile information becomes available. Investigators are responsible for briefing their study team and onward transmission to R&D office as appropriate.

## 11 PREGNANCY

Pregnancies (in a participant or partner) occurring within 30 days of the last IMP dose require expedited reporting. A Pregnancy Notification Form should be completed and faxed to the Trial Office within the same timelines as an SAE. Women who become pregnant should be withdrawn from the interventions at the earliest opportunity. All reported pregnancies should be followed and the outcome reported using the same form. If the outcome of the pregnancy meets any of the criteria for seriousness, it must also be reported as an SAE. Examples of pregnancy outcomes that are SAEs:

- Reports of congenital anomalies or developmental delay, in the foetus or the child.
- Reports of foetal death and spontaneous abortion.
- Reports of suspected adverse reactions in the neonate that are classified as serious.

## 12 DEFINING THE END OF TRIAL

For this study the end of the trial is defined as “The last visit of the last patient after a minimum of 8 years follow-up in the trial (LPLV)”.

The Sponsor and the Chief Investigator reserve the right to terminate the study earlier at any time. In terminating the study, they must ensure that adequate consideration is given to the protection of the participants' best interests.

## 13 STATISTICAL CONSIDERATIONS

### 13.1 Primary and Secondary Endpoints

**PRIMARY:** Time from randomisation to the first of the following:

- conversion from Barrett's oesophagus to adenocarcinoma of the oesophagus (event)
- high grade dysplasia (event)
- death by all causes (event)
- last known follow-up (no event)

**SECONDARY:** Time from randomisation to:

- adenocarcinoma of the oesophagus
- high grade dysplasia
- all-cause mortality
- cause-specific mortality

Also safety, quality of life, health economics, new tumours and molecular markers.

### 13.2 Sample size and power

#### *Original sample size statement*

The event rate in the UK is 0.98% (95% CI = 0.67 to 1.39%) (This is higher in the UK than the USA) however to be cautious we have agreed on 0.76%/year (approximately half way between the UK and USA).

Aspirin has a hazard ratio of 1.5 (33.3% effective) in preventing the colorectal cancer rate. Evidence from epidemiological studies suggests that aspirin may decrease BA rates with a hazard ratio of 1.6 to 10 (40-90%) (35-37). While we believe that current evidence indicates that aspirin is at least equally effective in the prevention of oesophageal adenocarcinoma as colorectal cancer, the role of PPI is more difficult to estimate for the reasons given previously. Therefore we have chosen a hazard ratio of 1.4 (28% effective) to assess weaker therapeutic effects.

Compliance to repeated endoscopy is excellent with over 90% of patients coping well with repeated examinations. Compliance to the therapy indicates that 90% manage well with no serious side effects to PPIs or low dose aspirin according to drug data sheet based on over 1 million patients for PPI and millions of people with over 50 years' experience for aspirin therapy. In addition evidence from other chemoprevention trials using 300mg of aspirin suggests that it is well tolerated over several years (< 5% side effects) UKcap study. Therefore a 20% non-compliance rate will be included in our calculations over and above losses calculated for loss to follow-up. Patients will be returning unused drugs to their local pharmacy every 6 months. The annual follow-up will be used to remind patients about the importance of compliance.

A total of 5000 patients (1250 in each intervention group) will allow us to detect a difference in conversion rates of 0.22% per year between the PPI and aspirin intervention. The sample size required was calculated using nQuery Advisor® Release 4.0 based on the following:

- Patients will be recruited over 2 years and followed up for a further 8 years.
- Exponential time to conversion with a constant event rate of at least 0.76% per year
- Conversion hazard ratio (drug response) of control to treatment is 1.4
- Power = 80% (2-sided test at 5% level of significance).
- No interaction between the effects of aspirin and PPI interventions.
- A 10% loss to follow-up from NHS HSCIC flagging
- A 20% non-compliance with medication
- Calculations adjusted for competing causes of mortality. A further proportion may take their medication but be lost to follow-up as they do not return their questionnaire and/or attend for surveillance endoscopy. This will not affect the primary outcome as all-cause mortality and conversion to BA will be assessed by the Office of National Statistics, which has almost complete follow-up of registered subjects (we have conservatively assumed a 90% follow-up rate).

#### *Exploratory sample size statement October 2008*

Due to protocol amendments and an expected restriction on the number of patients to be recruited, an exploratory sample size is presented at the request of the Funders. Since the trial recruited until the end of February 2009 in the UK rather than to the number calculated in the original sample size, this calculation should be considered as a guide to the power and treatment effect size the trial should achieve.

This exploratory sample size is calculated as per the original sample size, but with

- Annual rate of conversion of 1% (allowing for the composite primary endpoint of all-cause mortality and conversion to adenocarcinoma and conversion to high grade dysplasia.)

*Justification:* Using the National Statistics figures for 2005 based on the age and gender structure of the first 2046 patients recruited to AspECT gives a mortality rate in a year of 1.16%.

Using the UK Barrett's conversion rate to adenocarcinoma of at least 0.98% per year without treatment for 60% of the sample and 40% with a lower conversion rate of 0.66% (due to being female, have tongues of Barrett's metaplasia or only 1cm of Barrett's, or being <45 years old). Differing rates are not published for these patients so a rate of two thirds the UK conversion rate has been used) i.e. 0.85% conversion rate without treatment over the whole sample.

No good estimates of rates for conversion to high grade dysplasia for the UK could be found.

In this population, it is unlikely that the event rate for the composite primary endpoint in the control arm will be less than 1%.

- Hazard ratio as in colorectal cancer
- No adjustment for compliance
- the follow-up increased to 10 years (subject to available funding)

Apart from limited recruitment and checking the event rate using the age/sex structure, no information or estimates from the current trial are used.

A total of 2224 patients (approximately 556 in each intervention group) will allow us to detect a difference in conversion rates of 0.34% per year between low dose and high dose PPI and aspirin or no aspirin. This sample size was calculated using ARTMENU in STATA release 10.0 based on the following:

- Patients will be recruited over 3 years and followed up for a further 10 years (subject to available funding)
- Exponential time to conversion with a constant event rate of at least 1% per year without treatment
- Conversion hazard ratio (drug response) of control to treatment is 1.5 (1 year conversion rate 1% no or standard treatment vs 0.66% in the treated patients)
- Power = 80% (2-sided test at 5% level of significance)
- No interaction between the effects of aspirin and PPI interventions
- A 10% loss to follow-up from NHS HSCIC flagging

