## 14.1 Final analysis

This trial completed recruitment within 4 years of opening to recruitment. The DSMC will decide the time point for the final analysis. Final analysis is planned 8 years after the end of patient recruitment and will be guided by the fulfilment of the sample size calculation to be when there are at least 200 events and a median of at least 5 years follow up.

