2.5.3 Exploratory sample size statement October 2008

Due to protocol amendments and an expected restriction on the number of patients to be recruited, an exploratory sample size is presented at the request of the Funders. Since the trial will recruit until end Dec 2008 in the UK and possibly until the end of June in Canada rather than to the number calculated in the original sample size, this calculation should be considered as a guide to the power and treatment effect size the trial should achieve.

This exploratory sample size is calculated as per the original sample size, but with

- Annual rate of conversion of 1% (allowing for the composite primary endpoint of all cause mortality and conversion to adenocarcinoma and conversion to high grade dysplasia.)

Justification: Using the National Statistics figures for 2005 based on the age and gender structure of the first 2046 patients recruited to AspECT gives a mortality rate in a year of 1.16%.

Using the UK Barrett's conversion rate to adenocarcinoma of at least 0.98% per year without treatment for 60% of the sample and 40% with a lower conversion rate of 0.66% (due to being

AspECT

A phase III randomised study of Aspirin and Esomeprazole chemoprevention in Barrett's metaplasia

Funded by CR-UK, MRC, UHL and NCI

ISRCTN No.85156844

female, have tongues of Barrett's metaplasia or only 1cm of Barrett's, or being <45 years old. Differing rates are not published for these patients so a rate of two thirds the UK conversion rate has been used) ie 0.85% conversion rate without treatment over the whole sample.

No good estimates of rates for conversion to high grade dysplasia for the UK could be found.

In this population, it is unlikely that the event rate for the composite primary endpoint in the control arm will be less than 1%.

- HR as in colorectal cancer
- No adjustment for compliance
- the follow-up increased to 10 years

Apart from limited recruitment and checking the event rate using the age/sex structure, no information or estimates from the current trial are used.

A total of 2224 patients (196 events) (approximately 556 in each intervention group) will allow us to detect a difference in conversion rates of 0.34% per year between low dose and high dose PPI and aspirin or no aspirin. This sample size was calculated using ARTMENU in STATA release 10.0 based on the following:

- Patients will be recruited over 3 years and followed up for a further 10 years

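### The 2008 sample size statement prints a detectable difference of 0.34% per year that has 80% power only at a 1% composite rate, while its own components sum to about 2% per year

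*Protocol*

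**What the plan says.** The exploratory statement in Protocol 13.2, repeated in SAP 2.5.3, sets the control rate for the composite: "Annual rate of conversion of 1% (allowing for the composite primary endpoint of all-cause mortality" and the two conversion endpoints. As justification it reports that national statistics applied to the age and sex structure of the first 2046 patients "gives a mortality rate in a year of 1.16" per cent. It also derives a "0.85% conversion rate without treatment over the whole sample" for adenocarcinoma. It found no usable UK rate for high grade dysplasia (HGD). It then concludes that a composite control rate below 1% is unlikely.

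The listed assumptions are "Power = 80% (2-sided test at 5% level of significance") and "Conversion hazard ratio (drug response) of control to treatment is 1.5 (1 year conversion rate 1"% against 0.66%). The hazard ratio is carried over from colorectal cancer. The results sentence gives the detectable effect only as an absolute figure: the sample "will allow us to detect a difference in conversion rates of 0.34% per year between low dose and high dose PPI", and likewise for aspirin or none. The SAP adds the event count: "A total of 2224 patients (196 events").

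Protocol 14.1 plans the final analysis 8 years after recruitment ends and adds a guide: "when there are at least 200 events and a median of at least 5 years follow up".

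**The concern.** Mortality alone, at 1.16% per year, exceeds the 1% assumed for death, adenocarcinoma and HGD together. A rate set too low is cautious when the effect is a hazard ratio, because more events then arrive than were counted on. It is not cautious when the effect is a fixed absolute difference: the same 0.34% is a smaller relative effect on a larger base.

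The statement offers itself as a guide to the power and effect size to expect. A reader of a null result could therefore think that a benefit of 0.34% per year had been ruled out with 80% power, when at the plan's own component rates the trial would detect it about half the time or less. The 200-event guide in Protocol 14.1 also matches the 1%-based count of 196, so it says little about the information the trial should yield.

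**Working it through.** **Inputs from the documents.** Two-sided 5%, 80% power, hazard ratio (control to treatment) 1.5, 1% per year, 2224 patients split equally for each factor, 3 years' recruitment plus 10 years, 10% loss (Protocol 13.2); 196 events (SAP 2.5.3); 2513 patients recruited (Protocol 2); follow-up of 8 years, or up to 10 for those who re-consented (Protocol 5.2).

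**Assumptions of this check.** Exponential times; the 10% loss spread exponentially over the longest follow-up b, so η = −ln(0.9)/b; all patients in the comparison; effect on the whole composite. The number who re-consented is not given, so 8 years for all and a uniform spread of 8–10 years are both shown.

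**Formulas.**
- Event probability by time t: p = λ/(λ+η) × [1 − exp(−(λ+η)t)], averaged over the follow-up range.
- Events: D = N/2 × (p_control + p_treated).
- Power = Φ(√D/2 × ln HR − 1.96).

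**Step 1: reproduce the printed design.** Events needed for HR 1.5:
- Freedman: (1.96 + 0.842)² × (2.5/0.5)² = 196, as printed.
- Schoenfeld: 4 × (1.96 + 0.842)² / (ln 1.5)² = 191.

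With 2224 patients followed 10–13 years, the probabilities are 0.1038 and 0.0705, so D = 1112 × 0.1743 = 194. Power = Φ(13.92/2 × 0.4055 − 1.96) = Φ(0.86) = 80.6%. The calculation is sound on its inputs.

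**Step 2: the component sum.** Adenocarcinoma: 0.6 × 0.98 + 0.4 × 0.66 = 0.852. Composite before HGD: 1.16 + 0.85 = 2.01% per year. Death is 1.16/2.01 = 58% of this.

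**Step 3: change only the control rate.** Holding 0.34% per year gives 2.01 v 1.67, HR = 1.20. Holding HR 1.5 gives 2.01 v 1.34.

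| Patients, follow-up (10% loss) | Events, 0.34%/year | Power | Events, HR 1.5 | Power |
|---|---|---|---|---|
| 2224, 10–13 years | 405 | 46% | 371 | 97% |
| 2513, 8 years | 327 | 39% | 299 | 94% |
| 2513, 8–10 years | 366 | 43% | 335 | 96% |

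The most favourable setting tried, 2513 patients followed 10–13 years without loss, gives 479 events and 53% for 0.34% per year. Reaching 80% would take about 915 events.

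**Step 4: what the trial can detect at 2.01%.** With about 300–335 events, HR = exp(2 × 2.802/√D) is 1.38 to 1.36. Recounting events at the detectable effect itself gives 1.38 (8 years) and 1.35 (8–10 years). In absolute terms: 2.01 × (1 − 1/1.38) = 0.55 and 2.01 × (1 − 1/1.35) = 0.52% per year.

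**Step 5: dependence on the borrowed hazard ratio.** Suppose, as an assumption, that treatment cuts adenocarcinoma by one third and leaves death unchanged, with HGD ignored. The treated-to-control ratio is (1.16 + 0.85/1.5)/2.01 = 0.859. Power is about 28–34% in the three settings of the table.

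**Step 6: the 200-event guide.** With 2513 patients and uniform accrual from August 2005 to February 2009, 1% v 0.667% without loss gives about 197 events by February 2017, so 200 fits the 1% rate. At 2.01%, the expected date of 200 events runs from about November 2011 (2.01 v 1.67, no loss) to about January 2014 (both drugs at HR 1.5, 10% fewer events).

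**The case against.** The strongest reply is that the power input is a hazard ratio. The 0.34% is that ratio restated at a 1% base, both rates are printed, and the results sentence is conditional on the list below it. The 1% is worded as a minimum, in a statement labelled exploratory. All of this stands, and it rules out one inference a reader might draw from the table: that the trial's power is really 40-odd per cent. That is the power for the printed absolute difference only. For the hazard ratio actually assumed, the higher rate raises power to about 94–97%. What does not stand is that the results sentence is therefore harmless: it gives the effect on the one scale where the floor is not conservative.

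A second reply is that 2.01% is not a firm minimum. National mortality may overstate that of entrants selected for WHO status 0–1 with severe cardiac and respiratory disease excluded; the UK conversion rate carries an interval of 0.67 to 1.39%; and HGD would pre-empt some adenocarcinomas as well as add events. This is fair, and 2.01% should be read as the sum of the plan's own figures.

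A reader might also infer that 200 events must fall before the second interim analysis (August 2013 in SAP 2.3) and so bring the final analysis forward. The documents do not support that. The figure is a minimum joined to a median follow-up and a planned 8-year time point, the date depends on the assumed rate and effects, and the SAP schedules the final analysis for September 2017, after both interims.

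Finally, the definitive result will be a time ratio with its confidence interval (SAP 8.2), so a careful reader will not rely on the 2008 sentence. That limits the harm without making the sentence correct.

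**Conclusion.** The point holds for the printed absolute effect, which is wrong as written. The claim of 80% power for 0.34% per year is true only at a 1% control rate, about half the 2.01% that the statement's own components give. At 2.01% the power is roughly 39–46%, or up to about 53% with the largest sample and longest follow-up. The printed calculation itself reproduces, and its 1% floor is conservative for a hazard ratio of 1.5.

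The figures rest on a simple sum of components, constant hazards, no dilution from non-compliance and an effect on the whole composite. The last of these needs to be stated openly, because the hazard ratio comes from colorectal cancer while death makes up more than half of the expected events. The aspirin comparison excludes patients randomised for PPI only, so it has fewer than 2513 patients and somewhat less power than shown.

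On Protocol 14.1, the supportable conclusion is narrow: the 200-event figure matches the 1% rate and is not a measure of the information expected at about 2% per year.

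**What to change.** - **Protocol 13.2 and SAP 2.5.3.** Leave the October 2008 calculation in place, labelled as a lower-bound scenario. Add a restatement at the component-sum rate of about 2% per year before HGD: about 300–335 expected events for 2513 patients followed 8 to 8–10 years; 80% power for a hazard ratio of about 1.35–1.38 on the whole composite (about 0.5% per year); about 40–45% power for 0.34% per year.
- **Same place.** State that the colorectal hazard ratio of 1.5 is assumed to apply to a composite in which death is more than half of the expected events.
- **Protocol 14.1.** Note that the 200-event figure derives from the 1% rate and is a minimum only. State that the final analysis follows completion of planned follow-up (28 February 2017, with the 3-month allowance), consistent with the SAP's September 2017 start.

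The cost is wording only: no further patients, follow-up or data. The downside is that the stated detectable absolute difference becomes less favourable, about 0.5% instead of 0.34% per year.
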